Haemoglobin, creatinine, bilirubin, C-reactive protein, procalcitonin, leucocytes, platelets, lactate, arterial blood gas analysis (PaCO2, PaO2, FiO2, SO2, pH,

ScO2)

⁸ 24-h time period prior to randomisation

⁹ ITN, CVC, AC, RRT, mechanical ventilation, ECMO, haemodynamic monitoring

¹⁰ If AEs or SAEs are still "ongoing" after the end of treatment with the trial drug, observation will continue until the end of data collection (day 90).

Data on the vital status (alive/dead), if applicable date of death and cause of death, residence after discharge, if applicable, recording of "End of Life" decisions

² Basic data: sex, age, weight, height, time of hospital admission, time of ICU admission, type of admission, referring facility prior to ICU admission, etc. from the 24-hour period before randomisation, (data from ICU or normal ward)

2. Background to the clinical trial

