3.2 Secondary objectives and secondary endpoints

The purpose of the clinical trial is to secondarily investigate whether albumin administration and the maintenance of serum albumin concentrations of at least 30 g/l for 28 days after the onset of septic shock will influence 28- and 60-day mortality, ICU and hospital mortality rates, organ dysfunction/failure as assessed by the SOFA score, ICU and hospital lengths of stay, as well as ventilator- and vasopressor-free days. A cost-benefit analysis of the volume replacement therapy for the ICU stay up to a maximum of day 28 is another objective of this clinical trial.

Secondary end-points therefore are

- 28- and 60-day mortality,
- ICU and hospital mortality,
- organ dysfunction/failure as assessed by the SOFA-Score: recorded daily up to 28 days in the ICU after randomisation in the study,
- ICU and hospital lengths of stay.
- ventilator- and vasopressor-free days,
- cost-benefit of volume replacement therapy: collection of data on the use of human albumin and other colloids and crystalloids,
- · Total amount of fluid administration and total fluid balance, and
- safety-related parameters: occurrence of AEs and SAEs, especially anaphylactic shock, hypervolaemia, and pulmonary oedema.

4. Trial design

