6.3.2 Subsequent administration of the trial drug

Subsequent doses of the trial drug, starting from study day 1 will depend on the routine treatment day at each trial centre. A day begins when a new daily file is created at the trial centre. Study day 1 is thus defined as the 1st full day of treatment (24 h) after the day of randomisation.

Administration of the trial drug will be based on the serum albumin concentration measured each day. Dose adjustment will follow a predetermined schedule with the aim of maintaining a serum albumin concentration of at least 30 g/l.

Dose adjustment according to serum albumin concentration: ≥ 30 g/l: no administration

≥ 25 g/l and <30 g/l: 40 g over 1-2 h ≥ 20 g/l and <25 g/l: 60 g over 2-3 h <20 g/l: 80 g over 3-4 h

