6.5 Discontinuation of the trial interventions- discontinuation due to a medical reason

The decision to discontinue or to continue treatment with the trial drug from a medical point of view will be at the discretion of the treating physicians (members of the trial group).

Premature discontinuation of treatment with the trial drug does not lead to termination of the study. Further observation and documentation will be continued.

Human albumin is a normal component of human plasma and does not differ in its effects from physiological albumin. According to the current drug information brochure, toxicity tests for single-use human albumin in animals are of little relevance and do not enable determination of the toxic or lethal dose or a dose-response relation. The target serum albumin concentration in the clinical trial is within the normal range of human plasma albumin (mindestens 30 g/l), so that overdose is unlikely.

According to the current drug information brochure, the following adverse effects may occur with Albutein® 200 g/l or Plasbumin® 20:

- Mild reactions, such as flush, urticaria, fever, and nausea, are rare.
- In very rare cases, anaphylactic shock can occur.
- The possibility of transmitting an infection cannot be completely ruled out despite standard measures of preventing infections caused by drugs made from human blood or plasma. This also applies to all unknown or newly emerging viruses or other pathogens.

MIId reactions, such as flush, urticaria, fever and nausea, usually disappear quickly when the infusion rate is reduced or the infusion is stopped.

If such reactions occur, appropriate therapy should be initiated if clinically indicated. This includes therapy with antihistamines and symptomatic therapy.

In these cases, the trial drug should be subsequently administered over a longer period of time (up to twice the prescribed duration), with close monitoring of the relevant clinical

parameters. A new clinical evaluation and, if necessary, treatment with the trial drug should continue on the following day. If the reaction reoccurs, the trial preparation will be permanently stopped.

If anaphylactic shock occurs, infusion of the trial drug should be discontinued and adequate treatment should be initiated according to current recommendations for treating shock. Administration of the trial drug will be permanently stopped.

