7.5 Trial visits on trial days 1 to 28 after randomisation

These visits should only be performed if the patient is still being treated in the ICU.

- Blood sampling to determine the serum albumin concentration, including recording the time of blood sampling
- Blood samples for serum albumin concentration determination may be performed as part of the routine blood sampling procedure at the respective trial centre, provided that they are taken between 4:00 and 9:00 in the morning.
- Collection of data on infection, microbiology and anti-infective therapy
- Recording of the raw data for calculation of the SOFA score on the respective study day from the routine laboratory results (not for trial purposes); the "worst" daily value should be recorded
- Recording of concomitant medication with catecholamines and inotropes, diuretics, fluid therapy (including transfusion therapy, adjunctive sepsis therapy) on the respective trial day
- Recording of intensive care interventions (ITN, CIC, AC, RRT, mechanical ventilation, ECMO, haemodynamic monitoring) on the respective trial day
- Recording the amount of enteral and parentral fluid adminstration on the trial day
- Collection of routine laboratory data (not trial-related), taken between 4:00 9:00 in the morning: haemoglobin, creatinine, bilirubin, C-reactive protein, procalcitonin, leucocytes, platelets, lactate, arterial blood gas analysis (PaCO2, PaO2, FiO2, SO2, pH, ScO2)
- Recording of clinical parameters (body temperature, respiratory frequency and haemodynamic parameters), 24 h urinary output, other fluid loss on the trial day
- Capturing of AEs/SAEs and sepsis-related clinical events (continuous)
- Recording of vital status (live / dead)
- Albumin group: administration of the trial drug according to serum albumin concentration, dose adjustment according to the given scheme
- Data collection regarding administration of the trial drug (continuous), including information on the administered dose, interruption or discontinuation of the dose if necessary Note: After administration of the trial drug on day 28, no further doses are given.

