8.3 Duration of recording adverse events

Recording of AEs and sepsis-related adverse events begins at randomisation. Because the study drug is human albumin, which is a normal constituent of human blood plasma, and does not differ in its effects from physiologic albumin, recording and follow-up of AEs and SAEs for a maximum of 24 hours after the last dose of the trial drug is considered to be sufficient. Therefore, AEs and sepsis-related adverse events will be recorded

- in the albumin group until 24 h after the last dose of the trial drug and
- in the control group without albumin until day 28 after randomisation or until discharge from the ICU, if it occurs before day 28 after randomisation.

In the event that AEs or SAEs are still "ongoing" after the above dates, they will be tracked until maximum the end of data collection (Day 90). If they are "ongoing" on day 90, they are documented as "not recovered," "recovered with sequelae," or "unknown."

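### Recording of new adverse events ends 24 h after the last dose in the albumin arm but at ICU discharge or day 28 in controls, and the safety tables by arm do not allow for it

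*Protocol*

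**What the plan says.** **Recording window.** Protocol 8.3 covers AEs, SAEs and sepsis-related events and starts at randomisation in both arms. Recording then runs "in the albumin group until 24 h after the last dose of the trial drug and", as the second item, "in the control group without albumin until day 28 after randomisation or until discharge from the ICU", where discharge precedes day 28. The reason given is that recording "for a maximum of 24 hours after the last dose of the trial drug is considered to be sufficient", since albumin is a normal plasma constituent. After the cut-off, only events still ongoing are followed, to day 90 at most (8.3, and footnote 10 to the visit schedule in 1.6).

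**When the last dose falls.** Protocol 6.3.2 sets dosing from the daily serum albumin, with "≥ 30 g/l: no administration". Protocol 6.4 and 6.5 allow the drug to stop while observation continues; after a mild reaction, for example, "If the reaction reoccurs, the trial preparation will be permanently stopped".

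**Daily visits.** Protocol 7.5, for patients in the ICU on days 1 to 28, lists "Capturing of AEs/SAEs and sepsis-related clinical events (continuous" and sets no arm limit.

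**Analysis.** Protocol 3.2 makes "safety-related parameters: occurrence of AEs and SAEs, especially anaphylactic shock, hypervolaemia, and pulmonary oedema" a secondary endpoint. Protocol 11.3.2 plans frequency tables. SAP 6.8.1 plans frequency and incidence analyses, which SAP 6.2 presents by treatment group. No person-time, censoring or common-window rule is stated.

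**The concern.** A crude count of patients with an event depends on how long each patient is watched. Under 8.3 the control window follows the ICU stay, while the albumin window follows the last dose. The last dose depends on serum albumin and clinical course after randomisation. An albumin patient who reaches the target level, or whose drug is stopped, and who then stays in the ICU is no longer recorded for new events; a comparable control still is.

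The argument in 8.3 concerns how long a drug effect could take to appear. It does not make the two windows comparable, and the protocol deliberately collects AEs in controls (8.2) so that the arms can be set side by side. At stake is the between-arm reading of a listed safety endpoint, including hypervolaemia and pulmonary oedema.

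**Working it through.** **Step 1: the texts side by side.** The documents give no AE rate and no distribution of the last-dose day, so there is no plan figure to reproduce.

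- Last dose more than 24 h before ICU discharge or day 28: the albumin window is shorter than the control window.
- Dosing up to that point: the albumin window is up to 24 h longer.
- Albumin-arm patient never dosed: 8.3 states no end. This should be rare, because 6.3.1 requires a starting dose.
- Under 7.5 as worded, recording covers every ICU day to day 28 in both arms, so the windows are nearly equal.

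**Step 2: other rules that act on the same tables.** Under 8.2 a sepsis-related event is documented as an AE only if a link with the trial drug is suspected, which is possible only in the albumin arm. This can only add AEs there. SAP 2.3 analyses safety as treated, whereas Protocol 11.3.1 names the ITT group. Under the SAP, a control patient given albumin could be counted with the albumin arm while keeping the control recording window.

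**Step 3: illustration of the window effect alone.** All inputs are assumed except the 47% ICU mortality, which is in Protocol 8.2.

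- Equal true risk in both arms and a 14-day ICU stay.
- Recorded days d: control 14; albumin with last dose on day 7, 7 + 1 = 8; albumin dosed to discharge, 14 + 1 = 15.
- Constant hazard of 0.05 per day: P(d) = 1 − exp(−0.05d).
- Front-loaded hazard h(t) = 0.15·exp(−t/4), with H(d) = 0.6·(1 − exp(−d/4)): P(d) = 1 − exp(−H(d)).
- Death as a competing event, spread evenly over the 14 days at the same rate in both arms: m = −ln(1 − 0.47)/14 = 0.0453 per day. For the constant hazard, P(d) = 0.05/(0.05 + m) × [1 − exp(−(0.05 + m)d)]. For the front-loaded hazard, P(d) is the integral from 0 to d of h(t)·exp(−H(t) − mt), computed numerically.

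| Model | P(8) | P(14) | P(15) | All with gap, P(8)/P(14) | Half gap, half to discharge | All to discharge, P(15)/P(14) |
|---|---|---|---|---|---|---|
| Constant, no death | 0.330 | 0.503 | 0.528 | 0.65 | 0.429/0.503 = 0.85 | 1.05 |
| Front-loaded, no death | 0.405 | 0.441 | 0.443 | 0.92 | 0.424/0.441 = 0.96 | 1.005 |
| Constant, with death | 0.280 | 0.386 | 0.399 | 0.72 | 0.339/0.386 = 0.88 | 1.03 |
| Front-loaded, with death | 0.364 | 0.387 | 0.388 | 0.94 | 0.376/0.387 = 0.97 | 1.003 |

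Without death, the ratio equals 1 when the share of albumin patients with this gap is [P(15) − P(14)]/[P(15) − P(8)], which is 0.12 (constant) or 0.06 (front-loaded), the rest being dosed to discharge.

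**Step 4: sensitivity to window length.** With constant hazards of 0.02 or 0.05 per day and no death, 7 recorded days against 10 give 0.72 or 0.75; 7 against 28 give 0.30 or 0.39; 11 against 10 give 1.09 or 1.08.

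**Step 5: would a rate per recorded day repair it?** Under the constant hazard, yes: the ratio is 1.00. Under the front-loaded hazard, H(8)/8 = 0.519/8 = 0.0648 and H(14)/14 = 0.582/14 = 0.0416. The ratio is 1.56 although the true risk is equal, because the shorter window keeps only the high-risk days.

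**The case against.** The strongest reply is that the gap may hardly arise. Dosing is decided each morning, and a day at or above the target does not end treatment, so a site can often identify the last dose only in retrospect. Section 7.5 asks for continuous capture on every ICU day, and 8.2 has sepsis-related events entered at the daily visits in both groups. Sites that keep recording would make the windows nearly equal. This stands as a limit on the size. It does not remove the conflict: 8.3 is the only section that states a duration, it differs by arm, and after permanent discontinuation the last dose is known at once.

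SAP 6.8.1 also analyses daily assessed data by Day 1, Days 2–7 and Days 8–28, which limits the effect in the early bins. The bins carry no denominator for patients whose recording has ended, so the late bin is not repaired. Anaphylactic shock would be expected around an infusion, inside the 24 h, so hypervolaemia, pulmonary oedema and general SAEs are more exposed to the problem.

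A reader might infer that the AE and SAE tables will show albumin as safer than it is. The documents do not support that. The window effect points that way only for patients with a gap and reverses slightly for those dosed to discharge. The albumin-only conversion of sepsis-related events into AEs works in the opposite direction, and as-treated grouping can shift counts between arms.

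**Conclusion.** The point holds as a comparability defect in the safety reporting. Protocol 8.3 gives the arms different ends of recording, 7.5 does not match it, and no planned analysis allows for the difference. If 8.3 is followed, new late events are under-counted in albumin patients whose last dose precedes ICU discharge or day 28 by more than 24 h. Neither the net direction nor the size in the AE and SAE tables can be derived from the documents.

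The ratios above rest on assumed hazards, an assumed 14-day stay and an assumed last-dose day. They show that the effect can range from substantial to negligible; they do not predict the trial's tables.

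A reader might also infer that the trial's efficacy results are compromised. They are not: vital status is collected to day 90 in both arms, and SOFA, laboratory, intensive-care and fluid data follow the ICU visits without this cut-off. The matter should be corrected, but it does not touch the primary endpoint.

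**What to change.** 1. Reconcile Protocol 7.5 and 8.3, with a cross-reference, so that new AEs, SAEs and sepsis-related events are recorded in both arms at least from randomisation to ICU discharge or day 28, whichever is first. This also gives a never-dosed albumin patient a defined end.
2. Base the between-arm tables on that common window. Keep the existing recording to 24 h after the last dose where it runs later, so that no safety coverage is lost, and list those extra events separately.
3. For data already collected under 8.3, add to SAP 6.8.1 a time-to-first-event analysis, censored at the end of each patient's recording window, with death as a competing event. State that this censoring may be informative, since the last dose depends on clinical course. Prefer this to an overall rate per recorded day, which assumes a roughly constant hazard (working, step 5).

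Cost: a protocol and SAP amendment, which may need ethics-committee and federal-authority approval under the amendment rules in Protocol section 12, and slightly more AE entry for albumin patients who stay in the ICU after their last dose. The daily visits already take place.

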8.4 Documentation of adverse events

All AEs will be recorded promptly by the trial centres in the eCRF. Sepsis-related clinical events will be documented in the daily visits section, all others in the AE section of the eCRF.

Events which should not be documented as an AE:

- Medical or surgical interventions (diseases or symptoms that lead to a necessary intervention are documented as an AE)
- Interventions to treat a pre-existing condition that were already planned before consenting to the clinical trial.
- Daily fluctuations in the clinical picture,
- Normal progression of the disease severity of sepsis,
- · Illnesses that existed before consenting to the clinical trial (this will be documented as concomitant disease and not AEs).

Each AE is to be checked to see whether it meets the criteria for an SAE and, if necessary, proceed according to the SAE declaration procedure (see corresponding chapter 8.6).

At the trial centre, care should be taken to ensure that all persons involved in the treatment of participants are adequately informed about the responsibilities in the event of adverse events.

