5.2.2 Patients who are unable to consent

Because of the expected high severity of illness in the trial population, most of the eligible patients will be unable to consent. In this case, it will not be possible to obtain written consent from the patient prior to initiating the study-related measures.

In patients with septic shock, early therapy is a crucial determinant of prognosis of these patients. A therapeutic benefit from the intervention -albumin administration in the albumin group- can likely only be demonstrated if the clinical trial is started within the first few hours of the diagnosis of septic shock.

Since, according to international guidelines, early initiation of therapy is one of the essential standard therapies for severe sepsis and septic shock, it may be justified to begin the clinical trial in the existing emergency situation (septic shock) without informed consent of a legal representative or a guardian. According to AMG, participation is legally possible even without informed consent if this cannot be obtained due to an emergency situation. These patients can be included in the study according to § 41 Abs. 1 AMG (29) which states that: if informed consent cannot be obtained because of an emergency situation, treatment indicated to be given without delay to rescue the life of the concerned persons, to restore their health or to minimize their suffering, can be promptly initiated. Consent for further participation must be obtained as soon as possible and reasonable.

In this case, the trial centers should adopt the locally established procedure for including patients who are unable to consent and follow the recommendations of the local ethics committee. The presumed will of the patient should be considered. If she/he would refuse to participate, the patient should not be included in the clinical trial.

Patients unable to consent - with a guardian or legal representative

consent to participate in the clinical trial may be given in writing by the guardian or legal representative. A copy of the act of attorney or the identity card must be kept in the trial centre (ISF or separately).

If the guardian or the legal representative considers that the patient would not have wanted to participate in the trial, or if the guardian or the legal representative refuses participation, the patient will not be included in the clinical trial.

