The consultant must be a specialist and have at least 6 months experience in intensive care medicine. The consultant should not be involved in the clinical trial or belong to the study department and should not be part of the patient's care team. The consultant must justify his/her decision in writing. Thereafter, inclusion of the patient is possible. The investigator must initiate appointment of a legal representative no later than 72 hours after inclusion in the clinical trial. Written consent for continuation of the clinical trial must be obtained from this legal representative. If this does not occur within a maximum of 72 hours of the establishment of a legal representative or she/he refuses participation in the study, participation in the clinical trial will be terminated for this patient. If SAEs have occurred, they must be pursued further in accordance with the relevant requirements.

If the patient dies before a legal representative has been appointed or decided to participate in the study or not, this should be documented in the eCRF accordingly.

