6.3 Administration of the trial drug (only in the albumin group)

6.3.1 Start dose

Administration of the initial dose of the trial drug must be started within 6 to 24 hours after the beginning of the septic shock. A maximum of 2 hours may elapse between randomisation and the start of administration of the initial dose.

Before the initial dose is given, a blood sample must be drawn to determine the serum albumin concentration.

Starting dose: 60 g human albumin 20% (200 g/l, infusion solution) over 2-3 h

Application: The investigational product will be administered intravenously using an infusion device. The human albumin should not be mixed with other medications, whole blood or packed red blood cells.

The study drug is ready to use and can be administered intravenously directly or after dilution with an isotonic solution (e.g., 5% glucose or 0.9% sodium chloride). Albumin solutions should not be diluted with water for injections as this may cause haemolysis in the treated patients.

The solution should be clear or slightly opalescent. Infusion solutions that are cloudy or have sediment should not be used. This may suggest that the product is unstable or the solution is contaminated. After opening the packaging of each vial, the solution should be used immediately.

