7.2 Time of randomisation

Randomisation leads to the assignment of a participant to the albumin group or to the control group without albumin.

The randomisation day is defined as the treatment day on which the randomisation takes place. It ends when a new daily treatment sheet is created.

Randomisation must be performed within two hours of the written informed consent or confirmation of urgency of participation in the clinical trial with possible benefit to the patient by an independent consultant or other procedures established in the trial centre to include patients who are unable to provide informed consent

The randomisation is carried out by an automated internet-based service, which is provided by the Centre for Clinical Studies Jena (ZKS). The group assignment is retrieved via a validated electronic tool (PaRANDies) by the respective trial centre. The group assignment of the patient must be documented (patient record, e-CRF). Each participant will receive a randomisation number.

- Collection of data on infection, microbiology and anti-infective therapy
- Recording of clinical parameters (body temperature, respiratory haemodynamic parameters) at the time of randomisation (+/- 1 hour)
- · Recording of concomitant medication (catecholamines, inotropes, diuretics, fluid therapy including transfusion, adjunctive sepsis therapy) at the time of randomisation (+/- 1 hour)
- Collection of routine data from the laboratory (not trial-related), performed in the 24-h period before randomisation: haemoglobin, creatinine, bilirubin, C-reactive protein, procalcitonin, leucocytes, platelets, lactate, arterial blood gas analysis (PaCO2, PaO2, FiO2, SO2, pH, ScO2)
- Recording of intensive care interventions (ITN, CVC, AC, RRT, ventilation, ECMO, haemodynamic monitoring) at the time of randomisation (+/- 1 hour)
- Start capturing AEs, SAEs, sepsis-related clinical events

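### Section 8.4 dates pre-existing illness from consent, while section 8.3 starts AE recording at randomisation, which leaves a gap for patients enrolled by deferred consent

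*Protocol*

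**What the plan says.** Section 8.3 fixes the start of safety recording: "Recording of AEs and sepsis-related adverse events begins at randomisation". Section 8.4 then lists what is not to be documented as an AE. One bullet reads "Illnesses that existed before consenting to the clinical trial (this will be documented as concomitant disease and not AEs". A companion bullet excludes interventions for a pre-existing condition if they were planned before consent. Section 8.7, on pre-existing diseases, only refers back to 8.4.

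On consent, section 5.2.2 expects that "most of the eligible patients will be unable to consent", and says that in this case "it will not be possible to obtain written consent from the patient prior to initiating the study-related measures". Proxy consent beforehand is possible: "consent to participate in the clinical trial may be given in writing by the guardian or legal representative". Otherwise section 5.1.2 admits patients on an independent consultant's confirmation or another local procedure, with consent sought afterwards. Section 7.2 accordingly requires randomisation "within two hours of the written informed consent or confirmation of urgency of participation". On the consultant route, "The investigator must initiate appointment of a legal representative no later than 72 hours after inclusion in the clinical trial", and written consent is due within a further 72 h of the representative being established.

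For the albumin arm, section 6.3.1 states: "A maximum of 2 hours may elapse between randomisation and the start of administration of the initial dose".

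SAP section 6.8.1 tabulates AEs by category, intensity, relationship and outcome. It gives no rule on onset date.

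**The concern.** An illness cannot sensibly be both pre-existing and new after randomisation. For a patient enrolled by deferred consent, the two sections allow exactly that. Section 8.3 has opened the recording period, but section 8.4 still treats anything that arises before consent as concomitant disease.

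Two things are at stake. The first is completeness: AEs and SAEs are a secondary endpoint (section 3.2), and the affected window can include the start dose. The second is the nature of the cut-off. In an open-label trial the boundary between history and adverse event should be fixed no later than allocation. Here it can be a date set after allocation, and it depends on the local consent procedure.

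**Working it through.** The plan gives no figure to reproduce, so the check sets the dates and passages side by side.

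**1. Written consent before randomisation (patient or proxy).** Consent comes first and randomisation follows within 2 h. The 8.4 cut-off then precedes the 8.3 start, so no post-randomisation illness is excluded.

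**2. Deferred consent, consultant route.** Take inclusion as the time of the consultant's confirmation (t = 0). Taking it as randomisation would move the result by at most 2 h. Let c be the time from initiating the appointment to establishing the representative. Section 5.2.2 does not limit c on this route.
- Randomisation: at most 2 h (section 7.2).
- Start dose, albumin arm: at most 2 + 2 = 4 h (section 6.3.1).
- Latest permitted consent: 72 + c + 72 = 144 + c hours. With c = 0 this is 144 h, or 6 days.
- Latest consent minus latest start dose: 144 − 4 = 140 h, plus c.

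Where section 5.2.2 requires the appointment itself within 72 h (patients without a representative), c falls inside the first 72 h and the limit is 144 h. These are limits and not expected delays. A representative who consents the same day shortens the window to hours.

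**3. What happens to an event with onset in that window.**

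| Event | Governing text | Result |
|---|---|---|
| One of the eight listed drug effects (flush, urticaria, fever, nausea, anaphylactic shock, hypervolaemia, pulmonary oedema, transmitted infection) | 8.2, mandatory AE, no consent condition | Protected |
| Sepsis-related event, drug link suspected | 8.2 | AE, protected |
| Sepsis-related event, no link suspected | 8.2, recorded at daily visits | Not an AE by design, unaffected |
| Clinically relevant worsening of pre-existing non-sepsis disease | 8.2 | AE, protected |
| SAE before the representative decides | 5.2.2, to be pursued | Protected, although the seriousness check in 8.4 is attached to events already recorded as AEs |
| New illness, unlisted, not sepsis-related, not pursued as an SAE | 8.3 includes it, 8.4 excludes it | Unresolved conflict |

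Only the last row is exposed.

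**4. By arm.** The rule is worded identically for both groups. Only the albumin arm is assigned trial drug in the window, so an unlisted drug-caused event lost there would come from that arm. Background illness would be lost from both.

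**5. No consent date.** For patients without a representative who enter on provisional agreement, section 5.2.2 keeps those who die before a representative is appointed or consents in the analysis. For them the 8.4 cut-off has no value, whereas the 8.3 date always exists.

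**6. Does another passage settle it?** Section 7.1 collects concomitant diseases present at ICU admission. This makes misfiling less likely but adds a third reference date. SAP section 6.8.1 does not select by onset. No passage says which date governs.

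**The case against.** The strongest reply is that consent in 8.4 is shorthand for trial entry. The visit schedule in section 1.6 puts written consent before randomisation, the general remarks in section 7 allow trial measures only after consent, and the later act is usually called consent to continuation (sections 5.2.2, 6.4 and 7.6). On that reading 8.3 and 8.4 agree to within 2 h. This may well be what was meant, but the text does not secure it. Section 7.2 names consent and confirmation of urgency as alternatives, section 5.1.2 describes the later act as consent obtained retrospectively, and section 5.2.2 in one place refers to consent to the trial or to its continuation. Read strictly, the remark in section 7 would bar every deferred-consent patient, so it cannot be used to define the term.

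A second reply is that specific duties override a general exclusion: AE capture runs from randomisation (sections 7.2 to 7.4), the listed reactions must be recorded, and pre-consent SAEs are pursued. This stands, and it removes most of the apparent exposure. A reader might infer that early reactions to the start dose would be lost. The documents do not support that, because the list in section 8.2 covers every adverse effect that section 6.5 cites from the drug information brochure.

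A reader might also infer that most patients consent only after randomisation and the start dose. Section 5.2.2 says only that most cannot consent themselves. It does not say how many lack prior proxy consent, and the start dose concerns one arm.

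**Conclusion.** The inconsistency is real but narrow. Read literally, 8.4 files as concomitant disease a new, unlisted, non-sepsis illness that is not pursued as an SAE and that begins between randomisation and deferred consent. The window can reach 144 h plus court time on the consultant route. The conclusion rests on taking consent in 8.4 at its plain meaning, which the text permits but does not compel.

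Its size cannot be estimated. It is tempting to multiply a deferred share by the delay divided by the recorded days. With assumed shares of 51–90%, assumed delays of 1–6 days, an assumed 10 recorded days and a constant event rate, this runs from 0.51 × 1/10 = 5% to 0.90 × 6/10 = 54%. That is not the loss. It counts all events in the window, including the protected ones. The share, the actual delay and the 10 days are not in the documents; only the 6-day limit follows from their time limits. The true deferred share could lie below 51%.

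Nor do the documents show that consent dates differ by arm, so a bias in the AE comparison is possible but not established. Sample size, alpha and the primary mortality analysis are unaffected.

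**What to change.** In section 8.4, make randomisation the reference date in place of consent, both for pre-existing illnesses and for interventions already planned. Add a sentence that any illness starting or worsening after randomisation is assessed under section 8.2 in both arms, whatever the date or route of consent. In data management, add a check for concomitant diseases with onset after randomisation, so that they are reviewed and re-filed where needed.

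The cost is two wording changes, one added sentence and one date check, with no extra visits or patients. The small downside is that sites may have to re-file some early entries.
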